
Analysis of Primary Endpoints
	
This crossover study will follow a Williams design with 6 treatment sequences balanced for first order carryover effects. A mixed model analysis consisting of fixed effects of treatment, visit, and sequence, and the random effect of patient will be carried out.
 
The analysis of primary endpoints for BE will be performed with this model on the PP population which will include all patients in the PP population who have generated FEV1 data over 24 hours.
 
The 90% CI on the ratio of the T-to-R means will be constructed using Fieller's method. Bioequivalence (BE) will be declared if the 90% CI is entirely contained within the BE interval, 0.800 to 1.250.
 
Adequate study sensitivity will be demonstrated if the Test (T) and Reference (R) products are shown to be statistically superior to placebo (two-sided, p<0.05, by applying the mixed model analysis to the ITT population.

Analysis of Safety Endpoints
	
All safety endpoints will be tabulated by treatment on the safety analysis set without formal inferential statistics. AEs will be mapped using Medical Dictionary for Regulatory Activities (MedDRA) with respect to the system organ class and preferred term. Incidence of treatment-emergent AEs and serious adverse events (SAEs) will be tabulated. Observed and change from baseline in vital signs, physical examinations, HEENT and chest examinations, COPD exacerbations, and ECGs will be tabulated by study medication.

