### **4.2 SECONDARY OBJECTIVES**

The secondary objectives of this study are to evaluate the safety and tolerability of the Lupin Tiotropium Bromide Inhalation Powder and SPIRIVA HANDIHALER following single doses of 18 mcg in patients 40 years of age and older with COPD.

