#### **4.4.2 Safety Endpoints**

Safety will be assessed throughout Part 1 and Part 2 of the study by monitoring the following:

- adverse events (AEs)
- SABA (albuterol/salbutamol MDI) and concomitant medication use
- vital signs measurements
- physical examinations
- head, ears, eyes, nose, and throat (HEENT) and chest examinations
- COPD exacerbations
- 12-lead electrocardiograms (ECGs)

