### 9.2.2.7 Electrocardiography

A 12-lead ECG will be performed for Part 1 and Part 2 as indicated in **Schedule of Events, Table 9-1**. For Part 1, the ECGs will be collected prior to lung function assessments. Procedures for conducting ECGs are described in the ECG manual. The patient should be in a supine position and resting for at least 5 minutes. A qualified physician at a central diagnostic center will be responsible for interpreting the ECG. However, at the screening visit (visit 1), the Investigator will preliminarily interpret the ECG to determine if the patient is eligible to proceed with screening assessments; final interpretation of the ECG will be the responsibility of the central ECG reader. The Investigator is responsible for determining whether an abnormality is clinically relevant.

Patients should have an ECG that is normal or free of clinically significant findings at the screening visit (visit 1) and visit 2.

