### 9.3.3 Double-blind Treatment Period (Part 1)

#### 9.3.3.1 Visit 2

Visit 2 is the beginning of the double-blind treatment period and will be conducted as day 0 and day 1.

The following procedures and assessments will be conducted at visit 2:

#### Day 0

- perform HEENT and chest examination
- perform 12-lead ECG, prior to measuring predose FEV1
- perform urine pregnancy test for all female patients of childbearing potential
- perform vital signs measurements (blood pressure, heart rate, respiration rate, and body temperature) prior to measuring predose FEV1

- perform predose FEV1 measurements at 0 hours (30 and 15 minutes before administration of study medication); see permitted spirometry windows in [section 9.2.1.1](#)
- Re-establish stability limits
  - Two stability limits (at home and investigational center) will be re-established (see [section 9.2.1.1](#)).
- demonstration of albuterol/salbutamol MDI and study medication inhaler technique
- assess inspiratory flow rate via In-Check DIAL device
- dispense/collect study medication
- review randomization criteria
- randomization via IRT
- administration of study medication at the investigational center
- check for issues with study inhaler
- perform serial FEV1 measurements at the following time points: 5 and 30 minutes postdose, and at 1, 2, 4, 6, 8, 10, and 12 hours postdose; see permitted spirometry windows in [section 9.2.1.1](#)
- dispense/collect albuterol/salbutamol MDI (as needed)
- dispense/collect placebo trainer
- review ed diary/electronic flow meter instructions
- assess ed diary data
- collect ed diary/electronic flow meter, as applicable
- record AEs
- record COPD exacerbations
- record concomitant medications/therapies

The patient will continue using the ed diary/electronic flow meter throughout the remainder of Part 1 and asked to measure their lung function (FEV1) in the morning prior to administering COPD medication at approximately the same time each day. Patients should not perform FEV1 measurements on the home device prior to day 1, visit 3 (both day 21 and day 22) and visit 4 (both day 42 and 43). Patients will be asked to record EXACT symptom scores (see [Appendix C](#)) and albuterol/salbutamol MDI in their ed diary.

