#### **11.5.7.2 Vital Signs**

Vital signs, including blood pressure, heart rate, respiratory rate and body temperature, will be collected at the screening visit (visit 1) and all subsequent investigational center visits. Descriptive statistics for vital signs at screening and at treatment visits (visits 2 through 4 or ET for Part 1 and visits 7, 9, and 10 or ET for Part 2) will be provided.

For Part 1, the double-blind period, summary statistics will be provided by treatment received on the day of the measurement.

Summary statistics will be provided separately for Part 2, the open label extension.

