13.7 Safety Analyses

Safety analyses will be summarized by treatment for the safety population as defined in [Section 10.3](#) for Part 1 and Part 2 separately. Summary statistics (number of subjects, mean, standard deviation, median, minimum, and maximum) will be included for continuous variables. Summarizations of categorical variables will be presented in tabular form (number of subjects and percentages). Safety of drug regimen will be assessed for adverse events, serious adverse events (SAEs), COPD exacerbations, vital signs, physical examinations, HEENT and chest examinations, ECG recordings, SABA (albuterol/salbutamol MDI) and concomitant medication use.

Listings of all safety measurements will be provided.

Sponsor: Lupin Inc.
Protocol no: TB-DPI-301

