13.7.5 HEENT, Chest Examination, and Electrocardiograms (ECG)

For Part 1, during the double-blind period, abbreviated physical examination findings (HEENT and chest examinations) will be summarized for any clinically significant findings and significant changes from Visit 2. ECG results will be summarized by visit, and changes in overall clinical interpretation will be summarized.

For Part 2 of the study (open label extension), findings will be summarized for any clinically significant findings and significant changes from Visit 2.

Sponsor: Lupin Inc.
Protocol no: TB-DPI-301

HEENT and chest examination findings will be summarized by four 3 by 3 shift tables where the shift is from visit 2 to each of the 4 visits during treatment, 2 visits in Part 1 and 2 visits in Part 2.

Electrocardiography (ECG) findings will be summarized by four 3 by 3 shift tables where the shift is from screening (visit 1) to each of the 4 visits during treatment, 2 visits in Part 1 and 2 visits in Part 2.

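### Every Part 1 treatment-visit ECG is taken before that day's dose, yet the synopsis and SAP 13.7 tabulate ECGs by study medication

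*Protocol*

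**What the plan says.** **Objective and endpoint.** Protocol section 4.2 sets the secondary objective as safety and tolerability of Test and Reference "following single doses of 18 mcg in patients 40 years of age and older with COPD". Section 4.4.2 names the 12-lead ECG among the safety endpoints.

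**Timing.** Protocol section 9.2.2.7 states: "For Part 1, the ECGs will be collected prior to lung function assessments". The lists for visits 2, 3 and 4 in section 9.3.3 repeat this for days 0, 21 and 42 ("perform 12-lead ECG, prior to measuring predose" FEV1).

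**Tabulation.** The rules differ from place to place:
- Protocol synopsis, Analysis of Safety Endpoints: "Observed and change from baseline in vital signs, physical examinations, HEENT and chest examinations, COPD exacerbations, and ECGs will be tabulated by study medication".
- SAP 13.7: "Safety analyses will be summarized by treatment for the safety population". The same paragraph lists ECG recordings among the data covered.
- SAP 9.3: for summaries, Part 1 treatment means the dosing day and the day after it.
- SAP 13.7.5: "ECG results will be summarized by visit, and changes in overall clinical interpretation will be summarized", with shift tables from screening.
- Protocol 11.5.7.2, for Part 1 vital signs: "summary statistics will be provided by treatment received on the day of the measurement".

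**The concern.** A safety table by treatment is normally read as showing what happened after each treatment. If the Part 1 ECGs are tabulated that way, the Test and Reference columns hold recordings made before Test or Reference was given on that day. Any drug effect visible in such a recording could only come from an earlier period, and so possibly from a different drug. A reader of the report could take the table as comparative single-dose ECG data when it contains none.

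**Working it through.** The check is a comparison of schedule and analysis text, with some counting. The documents give no figure to reproduce.

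**1. Where the ECGs fall.** Table 9-1 (repeated as SAP Table 2) marks the ECG at visit 1, on days 0, 21 and 42, and at visits 7, 9 and 10. Days 1, 22 and 43 and the early termination visit are unmarked, and the visit lists agree. On each dosing day the ECG precedes the predose FEV1, which precedes dosing. Treatment-visit ECGs that follow that period's dose: 0 of 3 per patient.

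**2. Nearest ECG after each Part 1 dose.**
- Period 1 dose (day 0): the predose ECG on day 21 (+3), which is 21 to 24 days later.
- Period 2 dose (day 21): the predose ECG on day 42, again 42 − 21 = 21 days later plus any window.
- Period 3 dose (day 42): none in Part 1. Patients who enter Part 2 next have an ECG at visit 7, nominally 71 − 42 = 29 days later, after open-label Test has been taken daily from day 43.

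Part 2 uses Test only. Reference therefore has no scheduled ECG within about 21 days of a dose anywhere in the study.

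**3. What tabulation by treatment would do.** Under SAP 9.3, day 0, 21 or 42 belongs to the treatment given that day. Applied to ECGs through SAP 13.7, this labels each ECG with a drug taken after the recording. From the six sequences in Table 7-1, the immediately preceding randomized treatment would be:

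| Label given to the ECG | No earlier randomized dose | Preceded by placebo | Preceded by the other active |
|---|---|---|---|
| Test | A, E | B, C | D, F |
| Reference | B, F | D, E | A, C |

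With equal allocation each cell is 2/6, or one third.

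**4. Change from baseline.** SAP 9.1 makes baseline the last observation before dosing. If that is read period by period, the treatment-day ECG is itself the baseline and nothing follows it in the period. The change that the synopsis calls for then cannot be formed for a single dose.

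**5. By visit instead.** SAP 13.7.5 avoids the false label. Its by-visit tables still hold only predose recordings in Part 1 and mix the three treatments, so they do not compare Test with Reference. Its ECG shift tables are also miscounted: four (two visits per part), where the schedule and protocol 11.5.7.4 give 3 + 3 = 6.

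**6. Vital signs.** On days 0, 21 and 42 they too precede the predose FEV1. They are repeated on days 1, 22 and 43, alongside the 23 and 24 hour spirometry, so post-dose values exist. SAP 9.3 places those next-day values with the treatment just given. Protocol 11.5.7.2, read literally, does not.

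**The case against.** The strongest reply is that the ECG-specific text already does the sensible thing. SAP 13.7.5 summarizes by visit, protocol 11.5.7.4 uses visit-based shift tables, and protocol 11.5.7 omits ECGs from its list of summarized safety variables. Only the synopsis and the general opening of SAP 13.7 point to treatment. Protocol section 11 lets the SAP prevail over the protocol, and a specific clause usually outranks a general one. On this view, the one-third splits describe a table that may never be produced. Much of this stands: by-visit output is the likelier outcome. It does not settle the matter, because SAP 13.7 and 13.7.5 are in the same document, so precedence over the protocol cannot choose between them. The table shells are held separately. Neither rule tells the reader that the recordings are predose.

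Two further points stand. Predose ECGs have a stated use, in randomization criterion 7 and continuation criterion 5, so their timing is not in itself a fault. And safety summaries are descriptive: no passage plans a conclusion about comparative ECG safety.

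A reader might also infer that the post-dose vital signs are left without a treatment, or that day 43 vital signs of Part 2 entrants would be counted as Test. The documents do not support either. SAP 9.3 assigns days 1, 22 and 43 to the dose just given, and the SAP governs. Day 43 vital signs are a visit 4 procedure; section 9.3.4.1 places the first open-label dose after all visit 4 procedures, and visit 5 lists no vital signs.

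**Conclusion.** The concern holds for ECGs. None of the three Part 1 treatment-visit ECGs per patient follows that day's dose; the nearest after any Part 1 dose is about 21 days later, and the period 3 dose has none in Part 1. Tabulating these recordings by study medication, as the synopsis and SAP 13.7 say, misattributes them and contradicts SAP 13.7.5. The counts rest on the scheduled visits. The one-third splits also assume equal allocation and labelling by the dosing day as SAP 9.3 defines it.

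The point should not be widened in two directions. First, a reader might conclude that the single-dose safety objective has no post-dose data. It does: adverse events are assigned to the dosing day and the next day (SAP 13.7.1.1), and vital signs are repeated the next day. Second, a reader might assume that the HEENT and chest examinations are predose as well. They appear first in the visit lists but carry no instruction to precede spirometry, and the lists are not in time order: those for visits 3 and 4 put postdose spirometry ahead of dosing. Their timing is not established.

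**What to change.** 1. In the synopsis and SAP 13.7, remove Part 1 ECGs from the tabulation by study medication and follow SAP 13.7.5, by visit. Label each Part 1 treatment-visit ECG as predose and never show it under that day's treatment.
2. State that Part 1 ECGs give no information sooner than about 21 days after a dose and will not support single-dose or Test-versus-Reference ECG safety statements.
3. Align protocol 11.5.7.2 with SAP 9.3, so that vital signs on days 1, 22 and 43 are summarized under the treatment given the day before.
4. While SAP 13.7.5 is open, reconcile its number of ECG shift tables with the schedule.

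The cost is wording in the protocol, SAP and table shells, with no added procedures or visits. The one downside is that the stated reach of the ECG endpoint becomes slightly less favourable.

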## 2 LIST OF ABBREVIATIONS AND DEFINITION OF TERMS

Abbreviation	Definition
AE	adverse event
ANCOVA	analysis of covariance
ATS	American Thoracic Society
AUC 0-24	area under the curve from time zero to 24 hours postdose
CDER	Center for Drug Evaluation and Research
CDMS	clinical data management system
CFR	Code of Federal Regulation
CI	confidence interval
CRF	case report form
CRO	Contract research organization
COPD	chronic obstructive pulmonary disease
CV	coefficient of variation
CYP3A4	cytochrome P450 3A4
DALYS	Disability Adjusted Life Years
DPI	dry powder inhaler
ECG	Electrocardiogram
ERS	European Respiratory Society
ER-S	Evaluating Respiratory Symptoms
ET	early termination
EU	European Union
eCRF	electronic case report form
EXACT PRO (EXACT)	Exacerbations of Chronic Pulmonary Disease Tool Patient Reported Outcome
FDA	Food and Drug Administration
FEV 1	forced expiratory volume in the first second
GCP	Good Clinical Practice
GOLD	Global Initiative for Chronic Obstructive Lung Disease
HEENT	head, ears, eyes, nose, and throat
HIPAA	Health Insurance Portability and Accountability Act Authorization
HIV	human immunodeficiency virus
	
ICF	informed consent form
ICH	International Conference on Harmonisation
IEC	Independent Ethics Committee
IND	Investigational New Drug
IRB	Institutional Review Board
IRT	interactive response technology
ITT	intent-to-treat
IUD	intrauterine device

Iv	Intravenous
LABA	long-acting beta agonist
LAMA	long-acting anti-muscarinic agent
LCM	Local Clinical Management
LLT	lowest level term
LRI	lower respiratory infection
MedDRA	Medical Dictionary for Regulatory Activities
MDI	metered dose inhaler
NHANES III	National Health and Nutrition Examination Survey III
OTC	over-the-counter
P	Placebo
PD	pharmacodynamics(s)
PFTs	pulmonary function tests
PK	Pharmacokinetic
PT	preferred term
pMDI	pressurized metered dose inhaler
PP	per-protocol
PRN	as needed
R	Reference
RLD	reference listed drug
SABA	short-acting beta agonist
SAMA	short-acting anti-muscarinic agent
SAE(s)	serious adverse event(s)
SAP	statistical analysis plan
sNDA	Supplemental New Drug Application
SOC	system organ class
SUSAR	serious unexpected adverse reactions
T	Test
t max	time to maximum bronchodilator response
URI	upper respiratory infection
USA	United States of America
USC	United States Code

### 3 INTRODUCTION

#### 3.1 BACKGROUND

Chronic obstructive pulmonary disease (COPD) is a common preventable and treatable disease which is characterized by persistent airflow limitation that is usually progressive and is associated with an enhanced chronic inflammatory response in the airways and the lung to noxious particles or gases ([Global Initiative for Chronic Obstructive Lung Disease \[GOLD\] 2016](#)). Exacerbations and associated co-morbidities contribute to the overall severity in individual patients and present targets for treatment ([GOLD 2016](#)).

Chronic obstructive pulmonary disease (COPD) is the 4th leading cause of mortality globally ([GOLD 2016](#)) and this is set to increase in prevalence partially in response to historical smoking trends over past decades, although outdoor, occupational and indoor pollutants are also a major risk factor in development of COPD.

In the United States of America (USA) the estimated direct costs of COPD are around \$29.5 billion annually with indirect costs of \$20.4 billion; in Europe the burden of COPD makes up around 6% of the total healthcare budget. Fewer than 6% of the adult population have been diagnosed with COPD although there is a significant level of under diagnosis and the overall incidence is likely to be higher than this ([van den Boom 1998](#)).

Disease progression is generally associated with increasing levels for disability. The overall impact of disability and mortality can be quantified by Disability Adjusted Life Years (DALYs) which represent the sum of years lost due to premature mortality plus the sum of years lived with disability. Chronic obstructive pulmonary disease (COPD) is set to rise from the twelfth highest driver for DALYs in 1990 to the seventh highest by 2030 ([Mathers 2006](#)).

The goals of COPD therapy are focused initially on smoking cessation for subjects who continue to smoke followed by relief of symptoms, moderation of exacerbation frequency and severity and improvement in health quality and exercise tolerance ([GOLD 2016](#)).

Initial treatments for intermittent symptoms tend to be short-acting bronchodilators (SABAs) which are generally either beta-agonists (eg, albuterol) or anticholinergics (eg, ipratropium). The duration of action of SABAs is limited and as symptoms progress these are largely substituted by long-acting bronchodilators (LABAs), which include a variety of beta-agonists or anticholinergic medications. Long-acting bronchodilators (LABAs) can be used in isolation or as a combination of mechanisms for greater symptom control, or with the addition of broad spectrum anti-inflammatory medications such as inhaled corticosteroids for patients with more severe disease or at increased risk of exacerbations. The anticholinergic medications work by blocking the effect of acetylcholine on muscarinic receptors which results in smooth muscle relaxation and bronchodilation, which opens the airways and lowers airway resistance.

Tiotropium bromide is one of a number of long-acting anticholinergic medications approved for use with COPD. Tiotropium bromide under the trade name SPIRIVA® was approved by the Food and Drug Administration (FDA) in 2004 as a single-dose dry powder device delivered by the HANDIHALER® device for the long-term, once daily

maintenance treatment of bronchospasm associated with COPD. In 2009, a supplementary New Drug Application (sNDA) was granted for the indication to be expanded to include COPD exacerbation reduction. Tiotropium has been shown to reduce exacerbations and related hospitalization, improve health status (Barr 2005) and increase the effectiveness of pulmonary rehabilitation (Cheyne 2013), in addition to providing a maintenance therapy for bronchospasm.

Lupin Inc. is developing Tiotropium Bromide Inhalation Powder, equivalent to 18 mcg tiotropium/capsule (hereinafter referred to Lupin Tiotropium Bromide Inhalation Powder) as a substitutable product for SPIRIVA HANDIHALER. The strategy for the proposed clinical development of Lupin Tiotropium Bromide Inhalation Powder includes a total of 2 pivotal clinical studies: one assessing pharmacokinetic (PK) bioequivalence (BE) and one assessing pharmacodynamics (PD) BE of Lupin Tiotropium Bromide Inhalation Powder and SPIRIVA HANDIHALER. In addition, pilot studies are planned to examine the PK endpoints of Lupin Tiotropium Bromide Inhalation Powder compared to SPIRIVA HANDIHALER. Refer to section 3.2 regarding recent clinical experience with Tiotropium Bromide Inhalation Powder.

### **3.2 CLINICAL EXPERIENCE WITH TIOTROPIUM BROMIDE INHALATION POWDER ADMINISTERED BY A DRY POWDER HANDIHALER (DPI)**

SPIRIVA is marketed in 2 different delivery formats: as a single-dose DPI delivering 18 mcg of tiotropium from a capsule via the HANDIHALER device and as a multiple dose aqueous solution aerosolized mist inhaler delivering 1.25 or 2.5 mcg tiotropium per actuation via the RESPIMAT® device. These devices are marketed in the USA, Europe and, Japan under the same SPIRIVA trade name.

SPIRIVA has been found to be well tolerated with the most common side effect of dry mouth. Uncommon potential side effects include constipation, increased heart rate, blurred vision, glaucoma, urinary deficiency and urinary retention. Because Lupin Tiotropium Bromide Inhalation Powder is designed to be a substitutable product for SPIRIVA HANDIHALER, the safety profile is expected to be similar to SPIRIVA.

To date, 2 clinical studies (Study LBC-P-055-15 and LBC-P-006-15) with Lupin Tiotropium Bromide Inhalation Powder have been conducted.

Study LBC-P-055-15 was a randomized, open-label, single-dose, 3-period Phase 1, PK crossover study being conducted in healthy male subjects 18-45 years of age under fasting conditions. The primary objective of the study was to assess the systemic levels and relative bioavailability of a single orally-administered dose of tiotropium (36 mcg), administered as 2 inhalations from 1 batch of Lupin tiotropium capsules 18 mcg (×2 capsules) via both the LUPINHALER and HANDIHALER, and 1 batch of SPIRIVA capsules 18 mcg (×2 capsules) via the HANDIHALER.

Preliminary safety results from this study indicate that Tiotropium Bromide Inhalation Powder was well tolerated by the healthy subjects, ages 18 to 45 years. No SAEs were reported. The final statistical analyses and PK results are not available at this time. Because this was a pilot study used to screen a formulation of test product which is not

representative of the exhibit batch to be used in the pivotal BE in vivo studies, data is on file and not presented in this section.

Study LBC-P-0006-15 was a randomized, open-label, single-dose, 3-period Phase 1, PK crossover study being conducted in healthy male subjects 18-45 years of age under fasting conditions. The primary objective of the study was to assess the systemic levels and relative bioavailability of a single orally-administered dose of tiotropium (18 mcg), from 2 different batches of Lupin tiotropium capsules 18 mcg (×1 capsule) via the LUPINHALER, and 1 batch of SPIRIVA capsules 18 mcg (×1 capsule) via the HANDIHALER.

Preliminary safety results from this study indicate that Tiotropium Bromide Inhalation Powder was well tolerated by the healthy subjects, ages 18 to 45 years. No SAEs were reported. The final statistical analyses and PK results are not available at this time.

